#### **13.7.1.2.5 Other Analyses for Primary Variable(s)**

In order to further investigate the primary endpoint the following analysis will be done:

**Subgroup Analysis:** The incidence of the primary efficacy endpoint will be summarized by a number of covariates including age, gender, and race to examine their potential effects. Each of these factors will be analyzed statistically using a Cox proportional hazards model incorporating terms for treatment, the covariate and the treatment-by covariate interaction. The number of participants with outcomes, estimated hazard ratios, and associated 95% confidence intervals will be calculated within each of the subgroups generated by these analyses.

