**CLINICAL TRIAL PROTOCOL**  
**(Phase IV - Efficacy Trial)**

**Medical Device: FDA K031876 ELECTRO FLO PERCUSSOR, MODEL 5000**

**Non-randomized, multisite site, single arm study for the efficacy of current FDA 510k indication for adults between the ages of 18 and 55 (non-smokers).**

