#### **4.3 Rationale for this Trial Design**

Since this study is designed to illustrate the efficacy of the device for the current 510K indications in a single arm, large sample multisite study. A placebo control is not required since each subject will serve as a before and after treatment with measurable indicators.

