# **6. STUDY DESIGN**

## **6.1 Description of the Protocol**

The present study is designed as a multi-center, non-randomized, single-blind, one arm group trial with 70 participants per arm.

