## **7. SELECTION OF PROCESS OF PARTICIPANTS**

### **7.1 Number of Participants Planned**

Based upon the anticipated event rates, premature treatment discontinuation and expected relative efficacy, approximately 70 participants will be enrolled in the study, with approximately 70 participants in each arm.

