### **7.2 Inclusion Criteria**

- Previously diagnosed with cystic fibrosis (mild, moderate or severe)
- Prescribed (licensed medical provider) airway clearance device/system for at home, self-treatment for airway clearance
- Physically able to perform self-treatment or treatment by an at home medical provider

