### **8.3 Method of Assigning Participants to Treatment Group**

N/A - All included shall be assigned to the single arm.

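### The subgroup Cox model contains treatment and interaction terms that cannot be estimated in a single-arm trial

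*Protocol*

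**What the plan says.** Section 13.7.1.2.5 of the protocol has two parts. The incidence of the primary endpoint is to be summarised by several covariates, among them age, gender and race. Each is then to be analysed with a "Cox proportional hazards model incorporating terms for treatment, the covariate and the treatment-by covariate interaction", and hazard ratios with 95% confidence intervals are to be reported inside every subgroup. The endpoint being modelled is the one in section 13.7.1.1: time to the first adjudicated skin, allergic or new medical event.

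The design leaves no comparator. The title page calls the trial a "Non-randomized, multisite site, single arm study". Section 4.3 reasons that "A placebo control is not required since each subject will serve as a before and after treatment with measurable indicators". Section 6.1 describes a "non-randomized, single-blind, one arm group trial with 70 participants per arm", and section 8.3, on assignment to treatment group, reads "N/A - All included shall be assigned to the single arm". Section 7.1 states that "approximately 70 participants will be enrolled in the study".

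The SAP sets general conventions (summaries by treatment group, two-sided 5% tests) but has no subgroup section, so the protocol text stands uncorrected.

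**The concern.** A treatment-by-covariate interaction asks whether the difference between treated and untreated participants varies with the covariate. With nobody untreated there is no difference to vary. An analyst following section 13.7.1.2.5 would get either an error or a model from which the software has removed two of the three terms. The surviving hazard ratio compares one subgroup with another, for example women with men. It could be mistaken for a treatment effect or for evidence of effect modification.

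An analysis that cannot be run as specified will also be replaced by something else. If the replacement is chosen after the data have been seen, the subgroup results lose the protection of having been planned.

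**Working it through.** **Inputs.** N = 70 (sections 6.1 and 7.1). Treatment indicator T = 1 for everyone (section 8.3). Model terms: T, covariate z and T·z (section 13.7.1.2.5). The plan states no numerical result for this analysis, so there is no figure to reproduce.

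**Algebra.** The contribution of an event in participant i to the Cox partial likelihood is

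exp(b1·T_i + b2·z_i + b3·T_i·z_i) / Σ_j exp(b1·T_j + b2·z_j + b3·T_j·z_j), summed over those at risk.

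Put T = 1 throughout. The factor exp(b1) cancels, leaving exp((b2 + b3)·z_i) / Σ_j exp((b2 + b3)·z_j). So b1 does not appear at all, and b2 and b3 appear only as their sum. Within a subgroup z is constant too, and the contribution becomes 1/(number at risk), with no parameter left. That is why no treatment hazard ratio exists there.

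**Numerical check.** The Cox information matrix was computed at b = 0 for 70 simulated participants with a binary covariate, censoring at 21 days and 23 simulated events (event rate assumed; the documents give none). Columns are in the order T, z, T·z:

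| | T | z | T·z |
|---|---|---|---|
| T | 0 | 0 | 0 |
| z | 0 | 5.659 | 5.659 |
| T·z | 0 | 5.659 | 5.659 |

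The rank is 1 of 3. The same participants split into two hypothetical arms give rank 3 of 3. The entries depend on the simulated data; the zeros and the duplicated column do not.

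**Log-rank test (section 13.7.1.2.3).** At each event time with d events, n at risk and n1 of them in the treated group, the variance is proportional to d·(n1/n)·(1 − n1/n). With n1 = n this is 0. Observed minus expected is also 0, so the statistic is 0/0. The usual event-count formula, which divides by p(1 − p) for allocation share p, likewise divides by zero at p = 1.

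**What can be estimated.** Counts and incidence by subgroup, the Kaplan-Meier curve for the whole group, and the covariate effect b2 + b3 from a model with z alone.

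**Precision of the replacement.** The 95% half-width of a mean within-participant change, in SD units, is t(0.975, n − 1)/√n:

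- n = 70: 1.995/8.367 = 0.24
- n = 23 (70/3, equal thirds assumed): 2.074/4.796 = 0.43
- n = 10 (assumed): 2.262/3.162 = 0.72
- n = 7 (assumed): 2.447/2.646 = 0.93

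A comparison of three classes at N = 70 and two-sided 5% reaches 80% power (assumed target) only for Cohen's f of about 0.38. Such comparisons are descriptive.

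**The case against.** **Two-arm wording elsewhere.** Section 7.1 speaks of participants in each arm, Appendix 1 of matching placebos and Appendix 5 of double-blind conduct. None of these defines a second arm, and they conflict with the title page and sections 4.3, 6.1 and 8.3. They do not rescue the model.

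**Treatment as before versus after.** Section 4.3 treats each participant as their own control, so one might read the treatment term that way. But section 13.7.1.2.3 counts events only from allocation onward, and section 13.4.1.1 analyses participants by allocated group. No untreated person-time enters the model.

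**Not a total failure.** This stands. A reader might infer that the subgroup analysis yields nothing. In fact the incidence summaries are computable, and most software would drop the redundant columns and fit the covariate alone. The remaining model is simply not the one specified.

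**A carry-over from the primary test.** Also fair: the log-rank failure has the same cause and matters more. That argues for correcting both together.

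**CF severity.** Section 7.2 admits mild, moderate and severe disease, and a reader might infer that severity was wrongly shut out, that it is already on file, and that pooling across it distorts the mean SpO2 change because saturation cannot exceed 100%. The documents do not support this:

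- The covariate list is open, so severity is unnamed rather than excluded.
- Section 12.1.2 records compliance with the criteria. A yes/no entry satisfies that without a class, and no class definition is given.
- The model in section 13.7.1.2.5 concerns events, to which a saturation ceiling is irrelevant.
- No baseline saturation values, and no link from them to severity, appear anywhere.

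**Conclusion.** The specification is wrong as written. With treatment constant, its coefficient and the interaction are not identifiable (rank 1 of 3 for a single binary or continuous covariate), and the hazard ratios promised within subgroups do not exist as treatment effects. This rests only on there being one arm. It does not depend on event rates, effect sizes or software.

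The consequence is limited to a supporting analysis, part of which survives. The shared cause reaches the primary log-rank test, which gives the correction more weight than the subgroup model alone would.

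Adding severity is a reasonable suggestion, not the correction of an error. A reader might also expect subgroup summaries to show for whom the device works. In an uncontrolled before/after study they cannot, because differences in change between subgroups may reflect time, measurement or regression to the mean as well as the device. The precision figures assume the subgroup sizes shown; the documents give no subgroup split and no SD.

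**What to change.** In protocol section 13.7.1.2.5, delete the treatment and interaction terms and the within-subgroup hazard ratios. Replace them with:

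1. For the event composite of section 13.7.1.1: n/N with exact 95% confidence intervals by age group (cut-points fixed in advance), gender and race.
2. For the before/after outcomes of sections 5.1 and 5.2 (SpO2, FVC, FEV1): mean within-participant change with 95% confidence interval by the same factors, stating which pre- and post-treatment readings in the 21 days are used. This is needed because section 13.7.1.2.5 covers only the event composite, so deleting terms alone would give no subgroup result for the outcome in section 5.1.
3. A sentence labelling all of this exploratory and descriptive, with subgroup sizes shown and no claim about who benefits.

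Correct section 13.7.1.2.3 in the same amendment: keep the Kaplan-Meier curve and the crude rate, with confidence intervals, and drop the log-rank test. The step-down rule in section 13.7.1.2.4 depends on that p-value and needs a matching edit. Carry the text into the SAP.

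CF severity may be added as a factor if its classes are defined and a CRF field holds them. Percentage change should not be broken down by pre-treatment reading without a caveat: the baseline is also the denominator, and low starting values tend to rise by regression to the mean alone.

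The cost is wording in the protocol and SAP. Demographics are already among the baseline items in section 12.1.2. Only severity would need a definition and probably one new field. Section 13.1 already allows the plan to be revised before data lock.

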### **13.7.2 Secondary/Other Efficacy Variables**

#### **13.7.2.1 Description of Secondary/Other Variables**

Secondary endpoint: The composite cluster of the first occurrence, over the duration of study (randomization to study end date inclusive), of the following cluster of events:

#### **13.7.2.2 Statistical Analysis of Secondary/Other Variables**

The secondary and other endpoints will be analyzed using the same statistical methodology as for the primary efficacy endpoint (except for weight and waist circumference).

### **13.8 Safety Analysis**

For this morbidity/mortality trial, a benefit risk assessment is important. For this purpose safety analyses will be conducted on the same population (ITT) and using the same evaluation period as for efficacy analyses. (ie, from randomization until study end date)

### **13.8.1 Adverse Events**

#### **13.8.1.1 Definitions**

All adverse events recorded during the study will be coded according to Medical Dictionary for Regulatory Activities.

#### **13.8.1.2 Adverse Events**

Summaries will be done for the following types of AE:

- Number (%) of participants with any AE,
- Number (%) of participants with any new pulmonary condition,
- Number (%) of participants with any cardiology and neurologic
- Number (%) of participants permanently withdrawn from treatment.

All summaries will display, by treatment group, the overall frequency of participants with events, the frequency of participants with events within each primary system organ class and by preferred terms. For each preferred term and each system organ class a patient will be counted only once. For summaries on severe or medical device-related AE, for a given patient, the highest severity or relationship for a specific preferred term will be considered.

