### **5. STUDY OBJECTIVES**

#### **5.1 Primary Objective**

To specifically illustrate and measure both clinical and empirical efficacy described by (AARC) in the Clinical Practices Guidelines for Postural Drainage Therapy (1991) for external manipulation of the thorax for postural drainage therapy and the secretion clearance, or presence of atelectasis caused by mucus plugging.

Outcome measured by:

Percentage change of oxygen levels in the blood (pulse oximetry). SpO2 will be monitored using the standard pulse oximeter system (K131111). Change from baseline before treatment and measure again up to 3.5 hours after treatment.

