## **5.2 Secondary Objective**

To observe the quality of lung function that participants experience during the use of the device during the trial period.

Outcome measured by:

Percentage change of lung function. Evaluate expiratory forced vital capacity (FVC) and forced expiratory volume (FEV1) will be monitored with standard spirometer. Change from baseline before treatment and measure again up to 3.5 hours after treatment.

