### **9.1.2 Clinical Assessment Methods**

Primary: Measurements of before and after with pulse oximetry device and spirometer.

Secondary: Participant surveys completed.

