## **10.3 Waiver**

Expected efficacy endpoints specified in this trial (primary and secondary efficacy criteria) will not be considered as AEs and will not be subject to expedited regulatory reporting. They will be reported on specific outcome event forms, which should be sent within one (1) working day, by Email, to the Central Database number.

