### **13.8.3 Vital Signs**

Vital signs need to be within normal parameters for age of participant and remain so for the 21 day period of the trial. Vitals shall be taken before trial enrollment by prescribing physician.

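### Falls in SpO2, FEV1 or FVC after treatment have no planned count in the safety analysis, so respiratory worsening reaches the safety tables only if an investigator records it as an adverse event

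*Protocol*

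**What the plan says.** **Population.** Protocol 7.2 admits participants "Previously diagnosed with cystic fibrosis (mild, moderate or severe").

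**Respiratory readings.** Protocol 5.1 measures the primary objective by "Percentage change of oxygen levels in the blood (pulse oximetry"), with the instruction "Change from baseline before treatment and measure again up to 3.5 hours after treatment". Protocol 5.2 adds spirometry: "Evaluate expiratory forced vital capacity (FVC) and forced expiratory volume (FEV1) will be monitored with standard spirometer". Section 9.1.2 lists both under efficacy assessment: "Primary: Measurements of before and after with pulse oximetry device and spirometer". Sections 9.1.1 and 9.1.1.2 likewise name them as efficacy criteria. No section gives them a safety role.

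**Safety analysis.** Section 13.8 calls a benefit-risk assessment important. Its only pulmonary-specific line, in 13.8.1.2, is "Number (%) of participants with any new pulmonary condition". The same section also counts participants with any adverse event (AE) and breaks all summaries down by system organ class and preferred term. Sections 13.8.1.3 and 13.8.1.4 do this for serious events and for events leading to discontinuation. Section 13.8.2 declares laboratory evaluation not applicable. Section 13.8.3 requires vital signs to stay normal for 21 days, but the only measurement it specifies is this: "Vitals shall be taken before trial enrollment by prescribing physician".

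**Recording rule.** Section 10.1 defines an AE as any untoward medical occurrence and requires all AEs to be recorded. Section 10.3 says: "Expected efficacy endpoints specified in this trial (primary and secondary efficacy criteria) will not be considered as AEs". Those endpoints go on separate outcome event forms.

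**Summary statistics.** Protocol 13.4.1.3 and the SAP give mean, SD, median, minimum and maximum for continuous variables; the SAP adds a confidence interval and standard error. Neither asks how many participants declined.

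**The concern.** In people who already have cystic fibrosis, respiratory harm from a percussion device may well show as worsening of existing disease rather than as a new diagnosis. A line limited to new conditions does not clearly cover that. The trial does collect the objective readings that would show it, but the plan looks at them only as possible benefit.

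The benefit-risk balance that 13.8 asks for could then be lopsided: a rise in SpO2 or FEV1 would be presented as efficacy, while a fall in the same reading would have no safety count. An average can look favourable while several individuals decline, and the minimum shows one worst value, not how many fell. A single arm has no comparator to prompt the question.

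**Working it through.** The plan states no figure on this point, so there is none to reproduce. The check has two parts.

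**1. Can a fall in SpO2, FEV1 or FVC reach a safety table?**

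- *Directly from the readings:* no. No part of 13.8 names SpO2 or spirometry, sets a cut-off or counts decliners.
- *Through the pulmonary line:* only if the worsening is classed as a new condition. The term is undefined and all participants have cystic fibrosis.
- *Through the general AE, serious AE or discontinuation tables:* yes, but only once an AE has been recorded. Section 8.11 has participants record data on a personal smart device and send them to the Principal Investigator. No section tells the investigator to screen those readings for falls. Section 12.3 plans investigator follow-up by call, email and summary at the end of treatment.
- *Effect of 10.3:* section 9 makes SpO2 and spirometry efficacy criteria, and 10.3 says efficacy criteria are not AEs. A site could therefore decline to record a fall that 10.1 would have it record.

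**2. How many decliners can sit beside a favourable mean?**

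The only input from the documents is n = 70 (Protocol 6.1), with the two-sided 5% level (SAP). The means, SDs, normality and cut-offs are assumptions.

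Formulas: 95% CI = m ± t(0.975, 69) × s/√70, with t = 1.995. Share falling by at least c = Φ((−c − m)/s).

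Worked example for SpO2, m = 0.5, s = 2, c = 3 points: half-width = 1.995 × 2/√70 = 0.477, so the CI is 0.02 to 0.98. Share = Φ(−3.5/2) = Φ(−1.75) = 4.0%, and 70 × 0.040 = 2.8 participants.

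| Reading | Mean | SD | Cut-off | 95% CI of mean | Share falling | Of 70 |
|---|---|---|---|---|---|---|
| SpO2, points | 0.5 | 1.5 | 3 | 0.14 to 0.86 | 1.0% | 0.7 |
| SpO2, points | 0.5 | 2 | 3 | 0.02 to 0.98 | 4.0% | 2.8 |
| SpO2, points | 0.75 | 3 | 3 | 0.03 to 1.47 | 10.6% | 7.4 |
| FEV1, % change | 1.5 | 6 | 10 | 0.07 to 2.93 | 2.8% | 1.9 |
| FEV1, % change | 2 | 8 | 10 | 0.09 to 3.91 | 6.7% | 4.7 |
| FEV1, % change | 2.5 | 10 | 10 | 0.12 to 4.88 | 10.6% | 7.4 |

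Free of units: a mean gain that just reaches significance is 1.995/√70 = 0.238 SD. At that value Φ(−0.238) = 41% (about 28 of 70) change in the wrong direction, and Φ(−1.238) = 10.8% (7 to 8 of 70) worsen by more than 1 SD.

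**Precision of the missing count.** Exact (Clopper-Pearson) 95% intervals: 0/70 gives 0 to 5.1%; 5/70 gives 2.4% to 15.9%; 7/70 gives 4.1% to 19.5%.

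**Which reading is counted.** Payment per day of data in 8.11 suggests that readings may repeat over the 21 days. If 21 readings were independent (an assumption), a rule that flags any single fall would catch 1 − 0.960^21 = 58% of participants at a per-reading rate of 4.0%, and 1 − 0.894^21 = 90% at 10.6%. An any-fall rule would thus mostly count noise under that assumption, so the table must name its reading.

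**The case against.** A reader might infer that participants whose breathing worsens are absent from the safety results. The documents do not support that. The AE definition in 10.1 does not exclude worsening of existing disease, all AEs are to be recorded, and the any-AE, organ-class, serious-event and discontinuation tables are not limited to new conditions. This part of the objection stands in full: reported worsening is visible.

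A reader might also infer that the plan tests the mean change in SpO2 or FEV1 and would declare benefit from it. No section specifies such a test. Sections 13.7.1.1 and 13.7.1.2.3 describe a log-rank analysis of a composite of skin conditions, allergic reactions and new medical conditions, and 13.7.2.2 carries that method over to the secondary endpoints. The efficacy role of the readings rests on sections 5 and 9 alone.

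The reading of 10.3 can be contested. It may mean only the composite events of 13.7.1.1, and it reroutes endpoints to outcome forms rather than discarding them. The DMC receives outcome summaries (Appendix 5) and may request any analysis (6.4). These routes are real, but none commits to counting falls, and 10.3 is ambiguous because its parenthesis names the efficacy criteria. A sentence in 13.8.2 on changes from baseline stands under laboratory evaluations and names no respiratory reading. The semi-weekly surveys ask for opinion on efficacy (9.1.1.2).

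Finally, five of the six scenarios set the mean at 0.25 SD, just above the 0.238 threshold. They show what is arithmetically possible, not this trial's risk.

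**Conclusion.** The gap is narrow but real: 13.8 plans no count of falls in the only respiratory readings taken on the device, its pulmonary-specific line is confined to undefined new conditions, and 10.3 can be read against 10.1 on whether such a fall is an AE. Followed as written, the plan can under-count respiratory harm, because everything depends on an investigator recording the event.

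Under the assumed SDs and cut-offs, 1.0% to 10.6% of participants (about 1 to 7 of 70) could fall by the illustrative amount while the mean change is significantly positive. These are not estimates for this trial; the documents supply neither variability nor thresholds. Some such falls would be measurement noise, which a single arm cannot separate from harm. The change should be made, since it needs only data already collected.

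**What to change.** 1. In 13.8.1.2, widen the pulmonary line to any new or worsened pulmonary condition.
2. Reconcile 10.3 with 10.1, so that sites know whether a fall in SpO2 or spirometry is recorded as an AE. Which way this is settled is for the sponsor and investigators.
3. Add one table to 13.8: number and percentage, with exact 95% CI, of participants whose post-treatment SpO2, FEV1 or FVC fell by more than a cut-off that the sponsor and investigators fix before data are seen. State in advance:
   - the reading used, for example each participant's average or last pre/post change, not any single reading;
   - the population: ITT, as 13.8 sets for safety, with the number having paired readings as denominator.
4. Add a cumulative distribution plot of individual changes, and supply table and plot to the existing DMC.

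The cost is one table, one plot and two wording changes, with no new visit or procedure. The downside is that some counted falls will be noise, so the table should say so beside the interval.
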